5.11 Duration of Follow-up

Patients will be followed for disease status until documented disease progression, and for survival for 5 years after registration or until death, whichever occurs first.

6. Measurement of Effect

6.1 Antitumor Effect – Solid Tumors-RECIST

For the purposes of this study, patients should be re-evaluated for response every 12 weeks. Confirmatory scans for tumor response should also be obtained 6 weeks following initial documentation of objective response. In addition, patients with equivocal disease progression (e.g. a new lesion in the setting of major disease regression and the absence of or improvement in disease related symptoms and serum LDH) should have a scan confirming disease progression 4-6 weeks following the initial scan showing RECIST defined PD.

Response and progression will be evaluated in this study using the international criteria proposed by the revised Response Evaluation Criteria in Solid Tumors (RECIST) guideline (version 1.1) [Eur J Ca 45:228-247, 2009]. Changes in the largest diameter (unidimensional measurement) of the tumor lesions and the shortest diameter in the case of malignant lymph nodes are used in RECIST.

The following general principles must be followed:

1. To assess objective response, it is necessary to estimate the overall tumor burden at baseline to which subsequent measurements will be compared. All baseline evaluations should be performed as closely as possible to the beginning of treatment and never more than four weeks before registration.
2. Measurable disease is defined by the presence of at least one measurable lesion.
3. All measurements should be recorded in metric notation by use of a ruler or calipers.
4. The same method of assessment and the same technique must be used to characterize each identified lesion at baseline and during follow-up.

6.1.1 Definitions

Evaluable for Objective Response

Only those patients who have measurable disease present at baseline, have received at least one cycle of therapy, and have had their disease re-evaluated will be considered evaluable for response. These patients will have their response classified according to the definitions stated below.

NOTE: Patients who exhibit objective disease progression prior to the end of cycle 1 will also be considered evaluable.

Evaluable Non-Target Disease Response

Patients who have lesions present at baseline that are evaluable but do not meet the definitions of measurable disease, have received at least one cycle of therapy, and have had their disease re-evaluated will be considered evaluable for non-target lesion assessment. The response assessment is based on the presence, absence, or unequivocal progression of the lesions.

6.1.2 Disease Parameters

Measurable Disease

Measurable lesions are defined as those that can be accurately measured in at least one dimension (longest diameter to be recorded) as ≥ 20 mm by chest x-ray, as ≥ 10 mm with CT scan, or ≥ 10 mm with calipers by clinical exam. All tumor measurements must be recorded in millimeters.

NOTE: Tumor lesions that are situated in a previously irradiated area might or might not be considered measurable. If the investigator thinks it appropriate to include them, the conditions under which such lesions should be considered must be defined in the protocol.

Malignant Lymph Nodes

To be considered pathologically enlarged and measurable, a lymph node must be ≥ 15 mm in short axis when assessed by CT scan (CT scan slice thickness recommended to be no greater than 5 mm). At baseline and in follow-up, only the short axis will be measured and followed.

Non-measurable Disease

All other lesions (or sites of disease), including small lesions (longest diameter < 10 mm or pathological lymph nodes with ≥ 10 to < 15 mm short axis), are considered non-measurable disease. Bone lesions, leptomeningeal disease, ascites, pleural/pericardial effusions, lymphangitis cutis/pulmonitis, inflammatory breast disease, and abdominal masses (not followed by CT or MRI), are considered as non-measurable. Non-measurable also includes lesions that are < 20 mm by chest x-ray.

NOTE: Cystic lesions that meet the criteria for radiographically defined simple cysts should not be considered as malignant lesions (neither measurable nor non-measurable) since they are, by definition, simple cysts.

'Cystic lesions' thought to represent cystic metastases can be considered as measurable lesions, if they meet the definition of measurability described above. However, if non-cystic lesions are present in the same patient, these are preferred for selection as target lesions.

Target Lesions

All measurable lesions up to a maximum of 2 lesions per organ and 5 lesions in total, representative of all involved organs, should be identified as target lesions and recorded and measured at baseline. Target lesions should be selected on the basis of their size (lesions with the longest diameter), be representative of all involved organs, but in addition should be those that lend themselves to reproducible repeated measurements. It may be the case that, on occasion, the largest lesion does not lend itself to reproducible measurement in

which circumstance the next largest lesion which can be measured reproducibly should be selected.

A sum of the diameters (longest for non-nodal lesions, short axis for nodal lesions) for all target lesions will be calculated and reported as the baseline sum diameters. If lymph nodes are to be included in the sum, then only the short axis is added into the sum. The baseline sum of the diameters will be used as reference to further characterize any objective tumor regression in the measurable dimension of the disease.

Non-target Lesions

All other lesions (or sites of disease) including any measurable lesions over and above the 5 target lesions should be identified as non-target lesions and should also be recorded at baseline. Measurements of these lesions are not required, but the presence or absence of unequivocal progression of each should be noted throughout follow-up.

6.1.3 Methods for Evaluation of Disease

All measurements should be taken and recorded in metric notation using a ruler or calipers. All baseline evaluations should be performed as closely as possible to the beginning of treatment and never more than 4 weeks before registration.

The same method of assessment and the same technique must be used to characterize each identified and reported lesion at baseline and during follow-up. Imaging-based evaluation is preferred to evaluation by clinical examination unless the lesion(s) being followed cannot be imaged but are assessable by clinical exam.

Clinical Lesions

Clinical lesions will only be considered measurable when they are superficial (e.g., skin nodules and palpable lymph nodes) and ≥ 10 mm in diameter as assessed using calipers (e.g., skin nodules). In the case of skin lesions, documentation by color photography, including a ruler to estimate the size of the lesion, is recommended.

Chest X-ray

Lesions on chest x-ray are acceptable as measurable lesions when they are clearly defined and surrounded by aerated lung. However, CT is preferable.

Conventional CT and MRI

This guideline has defined measurability of lesions on CT scan based on the assumption that CT slice thickness is 5 mm or less. If CT scans have slice thickness greater than 5 mm, the minimum size for a measurable lesion should be twice the slice thickness. MRI is also acceptable in certain situations (e.g. for body scans).

Use of MRI remains a complex issue. MRI has excellent contrast, spatial, and temporal resolution; however, there are many image

acquisition variables involved in MRI which greatly impact image quality, lesion conspicuity, and measurement. Furthermore, the availability of MRI is variable globally. As with CT, if an MRI is performed, the technical specifications of the scanning sequences used should be optimized for the evaluation of the type and site of disease. Furthermore, as with CT, the modality used at follow-up must be the same as was used at baseline and the lesions should be measured/assessed on the same pulse sequence. It is beyond the scope of the RECIST guidelines to prescribe specific MRI pulse sequence parameters for all scanners, body parts, and diseases. Ideally, the same type of scanner should be used and the image acquisition protocol should be followed as closely as possible to prior scans. Body scans should be performed with breath-hold scanning techniques, if possible.

PET-CT

At present, the low dose or attenuation correction CT portion of a combined PET-CT is not always of optimal diagnostic CT quality for use with RECIST measurements. However, if the site can document that the CT performed as part of a PET-CT is of identical diagnostic quality to a diagnostic CT (with IV and oral contrast), then the CT portion of the PET-CT can be used for RECIST measurements and can be used interchangeably with conventional CT in accurately measuring cancer lesions over time. Note, however, that the PET portion of the CT introduces additional data which may bias an investigator if it is not routinely or serially performed.

Ultrasound

Ultrasound is not useful in assessment of lesion size and should not be used as a method of measurement. Ultrasound examinations cannot be reproduced in their entirety for independent review at a later date and, because they are operator dependent, it cannot be guaranteed that the same technique and measurements will be taken from one assessment to the next. If new lesions are identified by ultrasound in the course of the study, confirmation by CT or MRI is advised. If there is concern about radiation exposure at CT, MRI may be used instead of CT in selected instances.

Endoscopy, Laparoscopy

The utilization of these techniques for objective tumor evaluation is not advised. However, such techniques may be useful to confirm complete pathological response when biopsies are obtained or to determine relapse in trials where recurrence following complete response (CR) or surgical resection is an endpoint.

Tumor Markers

Tumor markers alone cannot be used to assess response. If markers are initially above the upper normal limit, they must normalize for a patient to be considered in complete clinical response.

Cytology, Histology

These techniques can be used to differentiate between partial responses (PR) and complete responses (CR) in rare cases (e.g., residual lesions in tumor types, such as germ cell tumors, where known residual benign tumors can remain).

FDG-PET

While FDG-PET response assessments need additional study, it is sometimes reasonable to incorporate the use of FDG-PET scanning to complement CT scanning in assessment of progression (particularly possible 'new' disease). New lesions on the basis of FDG-PET imaging can be identified according to the following algorithm:

- a. Negative FDG-PET at baseline, with a positive FDG-PET at follow-up is a sign of PD based on a new lesion.
- b. No FDG-PET at baseline and a positive FDG-PET at follow-up: If the positive FDG-PET at follow-up corresponds to a new site of disease confirmed by CT, this is PD. If the positive FDG-PET at follow-up is not confirmed as a new site of disease on CT, additional follow-up CT scans are needed to determine if there is truly progression occurring at that site (if so, the date of PD will be the date of the initial abnormal FDG-PET scan). If the positive FDG-PET at follow-up corresponds to a pre-existing site of disease on CT that is not progressing on the basis of the anatomic images, this is not PD.
- c. FDG-PET may be used to upgrade a response to a CR in a manner similar to a biopsy in cases where a residual radiographic abnormality is thought to represent fibrosis or scarring. The use of FDG-PET in this circumstance should be prospectively described in the protocol and supported by disease-specific medical literature for the indication. However, it must be acknowledged that both approaches may lead to false positive CR due to limitations of FDG-PET and biopsy resolution/sensitivity.

NOTE: A 'positive' FDG-PET scan lesion means one which is FDG avid with an uptake greater than twice that of the surrounding tissue on the attenuation corrected image.

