_____ 3.2.4 Patients must have recovered from adverse events (toxicities resolved to grade 1 or less) of prior therapy. Patients with immune related toxicities from ipilimumab + nivolumab may continue onto Step 2 even if still on steroids to control side effects, so long as toxicity has resolved to grade 1 or less.

_____ 3.2.5 Patients must have discontinued radiation therapy prior to registering to Step 2 of the study and recovered from any adverse events associated with treatment. Prior surgery must be ≥ 2 weeks from registration to Step 2 and patients must be fully recovered from post-surgical complications.

_____ 3.2.6 Patients are ineligible if they have any currently active and definitive CNS metastases. Patients who have treated brain metastases (with either surgical resection or stereotactic radiosurgery (SRS)) could be eligible to proceed. Patients crossing over from Arm B (dabrafenib/trametinib) to Arm D (nivo/ipi) must not have taken any steroids ≤ 10 days prior to Step 2 registration for the purpose of managing their brain metastases. Patients with only Whole Brain irradiation for treatment of CNS metastases are ineligible. Patients with definitive CNS metastases treated with only WBRT are ineligible. Patients with potential CNS metastases that are too small for treatment with either SRS or surgery (e.g. 1-2 mm) and/or are of uncertain etiology are potentially eligible, but need to be discussed with and approved by the Study PI.

Rev. Add13

_____ 3.2.7 Patients must not have other current malignancies.

Rev. Add13

_____ 3.2.8 Women must not be pregnant or breast-feeding, as the effects of ipilimumab + nivolumab or dabrafenib + trametinib on the developing human fetus are unknown. All females of childbearing potential must have a blood test or urine study within 2 weeks prior to registration to Step 2 crossover to rule out pregnancy.

Rev. Add10

A female of childbearing potential is anyone, regardless of whether they have undergone tubal ligation, who meets the following criteria: 1) has not undergone a hysterectomy or bilateral oophorectomy; or 2) has not been naturally postmenopausal for at least 24 consecutive months (i.e., has had menses at any time in the preceding 24 consecutive months).

Female of child bearing potential? _____ (Yes or No)

Date of blood test or urine study_____

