2. There is no LDH cutoff at time of crossover.

Patients may undergo local therapy (e.g. RT or surgery) for treatment of local disease progression, but still must meet eligibility criteria regarding treatment interval before initiating crossover therapy.

Patients who are more than 4 weeks from previous staging CT scan at time of crossover should have a repeat staging prior to initiating crossover therapy.

Rev. 12/15
Rev Add 15

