6.1.4 Response Criteria

6.1.4.1 Evaluation of Target Lesions

Complete Response (CR)

Disappearance of all target lesions. Any pathological lymph nodes (whether target or non-target) must have reduction in short axis to < 10 mm. To be assigned a status of complete response, changes in tumor measurements must be confirmed by a repeat assessment performed no less than six weeks after the criteria for response is met.

Partial Response (PR)

At least a 30% decrease in the sum of the diameters of target lesions, taking as reference the baseline sum diameters. To be assigned a status of partial response, changes in tumor measurements must be confirmed by a repeat assessment performed no less than six weeks after the criteria for response is met.

Progressive Disease (PD)

At least a 20% increase in the sum of the diameters of target lesions, taking as reference the smallest sum on study (this includes the baseline sum if that is the smallest on study). In addition to the relative increase of 20%, the sum must also demonstrate an absolute increase of at least 5 mm.

NOTE: The appearance of one or more new lesions is also considered progression, See Section [6.1.4.2](#).

Patients with equivocal disease progression (e.g. a new lesion in the setting of major disease regression and the absence of or improvement in disease related symptoms and serum LDH) should have a scan confirming disease progression 4-6 weeks following the initial scan showing RECIST defined PD. Patients may continue on protocol therapy until repeat scan confirms PD. If repeat scan does not confirm PD, patients should proceed with treatment and evaluation as directed by the protocol with the confirmatory scan (if between 4 and 6 weeks from last scan) being counted as the 6 week interval scan.

Stable Disease (SD)

Neither sufficient shrinkage to qualify for PR nor sufficient increase to qualify for PD, taking as reference the smallest sum diameters while on study. (Note: a change of 20% or more that does not increase the sum of the diameters by 5 mm or more is coded as stable disease)

To be assigned a status of stable disease, measurements must have met the stable disease criteria at least once after study entry at a minimum interval of 24_ weeks.

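### Section 6.1.2 requires protocol-defined conditions for irradiated lesions but none are given, so radiotherapy shrinkage can be scored as response after crossover; the caliper rule for palpable nodes also conflicts with the 15 mm node rule

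*Combined protocol and SAP*

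**What the plan says.** **Irradiated lesions.** A note in Section 6.1.2 leaves it open whether a lesion in an irradiated area is measurable. It adds that, if the investigator wants to include one, "the conditions under which such lesions should be considered must be defined in the protocol". No such conditions appear in Section 6.1 or elsewhere in the supplied text.

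**Radiotherapy around crossover.** Section 5.1.5 says: "Patients may undergo local therapy (e.g. RT or surgery) for treatment of local disease progression". The same sentence goes on to require that the eligibility criteria on treatment interval still be met. Section 3.2.5 says: "Patients must have discontinued radiation therapy prior to registering to Step 2 of the study", with recovery from its adverse events, but names no number of days. Section 3.2.1 asks that the Step 1 criteria be met again at crossover apart from listed exceptions, and 3.1.10 sets at least 1 week off radiotherapy.

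**Scan and baseline.** Sections 3.2.2, 3.2.3, 5.1.5 and 7.1.1 (footnote 6) accept staging up to 4 weeks old at crossover. Section 9.4 recalculates the response baseline at crossover and leaves patients without measurable disease at that point out of the response assessment.

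**Nodes.** Section 6.1.3 treats clinical lesions as measurable only when they are "superficial (e.g., skin nodules and palpable lymph nodes) and ≥ 10 mm in diameter as assessed using calipers". Section 6.1.2 accepts lesions "≥ 10 mm with calipers by clinical exam" and gives a 15 mm short-axis minimum for nodes on CT. It then says that "small lesions (longest diameter < 10 mm or pathological lymph nodes with ≥ 10 to < 15 mm short axis), are considered non-measurable disease". For complete response, 6.1.4.1 says: "Any pathological lymph nodes (whether target or non-target) must have reduction in short axis to < 10 mm".

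**The concern.** Response rate is a named secondary outcome. Objectives 2.2.4 and 2.2.5 ask whether each regimen keeps its activity after the other has been given, and Section 9.4 answers by comparing A with D and B with C. If some of the shrinkage counted in C or D was produced by radiotherapy given at local progression, those arms look more active than the drugs made them, and a real loss of activity after crossover is harder to see. The missing rule also decides who has measurable disease at crossover, and so who is in the denominator.

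The nodal wording raises a smaller issue of the same kind. Two sites could classify the same 12 mm palpable node differently, which affects Step 1 eligibility under 3.1.6, the target-lesion sum and the Step 2 response denominator.

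**Working it through.** The plan states no figure on this point, so the check is to set the provisions side by side, with threshold arithmetic for the nodes.

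**1. Can radiotherapy fall between the baseline scan and the start of Step 2 drugs?**
- Oldest acceptable scan: 4 weeks = 28 days before Step 2 registration.
- If the 1-week rule of 3.1.10 carries over through 3.2.1, radiotherapy must stop at least 7 days before. The window after the scan is 28 − 7 = 21 days.
- If 3.2.5 stands alone, the window is up to 28 days.
- Re-staging is required only when the last CT is more than 4 weeks old. Nothing requires a scan after radiotherapy.
- Section 5.7 bars local anti-cancer treatment while study drugs are being received, which does not cover this window.

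The answer is yes under either reading. Even when the scan does follow radiotherapy, a lesion still regressing from it may be chosen as a target, because 6.1.2 sets no condition.

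**2. Step 1.** Radiotherapy may stop 1 week before entry (3.1.10) and scans may be 4 weeks old (3.1.6, 7.1), so the same 21-day window exists.

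**3. Effect on response.** Let r be the true Arm D response rate, f the fraction with recently irradiated target lesions, and c the share of non-responders among them who are scored as responders. Then observed D = r + (1 − r) × f × c. None of the three is in the documents. As an illustration only, assume true rates of 50% in A and 30% in D, with the planning numbers of 150 and 100 from Appendix XVI. Exact power is for a two-sided Fisher test at 0.05:

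| f | c | Observed D | Power |
|---|---|---|---|
| 0 | – | 30% | 88% |
| 5% | 0.5 | 31.75% | 80% |
| 5% | 1 | 33.5% | 71% |
| 10% | 0.5 | 33.5% | 71% |
| 10% | 1 | 37% | 49% |
| 15% | 0.5 | 35.25% | 61% |
| 15% | 1 | 40.5% | 28% |

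The spread shows that the result is driven by f and c, which are unknown.

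**4. Nodes.** Nodal CR needs a short axis under 10 mm; PR needs a 30% fall in the target sum. In whole millimetres, the change from baseline b to 9 mm is (b − 9)/b:

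| Baseline (mm) | Change (mm) | Change (%) |
|---|---|---|
| 10 | 1 | 10.0 |
| 11 | 2 | 18.2 |
| 12 | 3 | 25.0 |
| 13 | 4 | 30.8 |
| 14 | 5 | 35.7 |
| 15 | 6 | 40.0 |

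Nodes of 10–12 mm reach the nodal CR size on less than the 30% needed for PR. The CR rule covers target and non-target nodes alike, so this is true however 6.1.3 is read. Section 6.1.3 affects only whether such a node is measurable and enters the target sum.

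**The case against.** **The note is restrictive.** It allows inclusion only under protocol-defined conditions, so with none defined a site could fairly read it as exclusion. That is a natural reading, but the note also says such lesions may or may not be measurable, and nothing tells sites which applies. A reader might infer that the plan simply leaves irradiated lesions to the investigator; it does not go that far. The defect is that the conditions it calls for are missing.

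**There is an interval.** A reader might infer that radiotherapy may run up to the day of Step 2 registration. Section 5.1.5 requires the interval criteria to be met, and 3.2.1 may bring in the 1-week rule. The documents leave the interval unclear and the sections need reconciling, but the 21-day window remains even with 1 week.

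**The nodal text.** A reader might infer that the plan permits 10–14 mm palpable nodes as measurable, and that a complete response can then follow from a millimetre or two of measurement error. The documents do not support this. Section 6.1.2 classes such nodes as non-measurable without limiting the method, 6.1.3 states a necessary condition only, and imaging is preferred. A patient-level CR also needs every other lesion gone and confirmation at least 6 weeks later. What stands is an inconsistency between sections.

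**It can be examined later.** Appendix XIII says that types and dates of radiation are captured through the parent protocol, and baseline target measurements are recorded, so affected patients can be flagged. This stands, although the appendix does not say that the irradiated site is recorded.

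**The bias may not be one-sided.** Recent radiotherapy is also possible at Step 1, which would raise response in A or B and partly offset the effect in A vs D and B vs C. This stands as a caution on net size. Radiotherapy for local progression, however, is provided for expressly at crossover.

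**Conclusion.** The irradiated-lesion gap is real. The plan sets itself a requirement and does not meet it, and its own crossover, staging and baseline rules then allow radiotherapy shrinkage to be credited to the drugs in Arms C and D. The likely direction is to flatter activity after crossover in the A vs D and B vs C response comparisons.

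The size cannot be stated. The documents do not say how many patients have radiotherapy near crossover or how many such lesions become targets. A reader might infer a large loss of power from the illustration above, but it rests on assumed response rates and an assumed irradiated fraction, and its worst rows count every irradiated non-responder as a responder. Appendix XVI also reports that crossover was lower than anticipated, so 100 patients in Arm D may be too many.

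Only secondary response comparisons are affected; the primary 2-year OS rate does not depend on RECIST. The nodal inconsistency is a lesser point that bears on measurable-disease status, target sums and the Step 2 denominator. Correcting it leaves the nodal CR threshold as it is.

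**What to change.** 1. Replace the note in Section 6.1.2 by: *Lesions in a previously irradiated field are non-target unless growth has been documented after completion of radiotherapy.* Apply it at both the Step 1 and Step 2 baselines.
2. Require the scan used as the response baseline to follow any local therapy.
3. Reconcile 3.2.5 with 3.2.1, 3.1.10 and 5.1.5 so that the radiotherapy interval before Step 2 is stated once.
4. Where baselines are already recorded, apply the rule in item 1 as a sensitivity analysis using the captured radiation dates. If the irradiated site is not recorded, flag at patient level.
5. In Section 6.1.3, state that the 15 mm short-axis rule applies to all nodes, whatever the method of measurement.

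The cost is a few sentences in Section 6.1, a repeat scan for some patients who receive local therapy after staging, and one sensitivity analysis. A few patients whose only lesion is a small node or an irradiated lesion would no longer count as having measurable disease. One limit remains: an irradiated non-target lesion that disappears still helps towards CR, although CR also requires the target lesions to meet their criterion.
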